Specific Aim 1. To assess the efficacy of pain coping skills training in reducing knee pain and improving function. Our two primary hypotheses (to be tested in the clinical trial) are the following:

- **Hypothesis 1a.** Pain coping skills training is more effective than arthritis care education in *decreasing knee pain during functional activities*.
- **Hypothesis 1b.** Pain coping skills training is more effective than usual care in *decreasing knee pain during functional activities*.

We also will examine **one secondary (hyp. 2) and one tertiary (hyp. 3) hypothesis**.

- **Hypothesis 2.** Pain coping skills training is more effective than arthritis education or usual care in improving self-reported function, physical performance, pain intensity, pain catastrophizing, and patient global ratings of improvement.
- **Hypothesis 3.** Pain coping skills training will reduce direct medical costs and indirect (i.e. patient time) costs relative to arthritis care education and usual care. When accounting for costs associated with pain coping skills training, the intervention will be cost saving or cost-effective relative to arthritis care education and usual care as measured by the incremental cost per quality-adjusted life-year.

Specific Aim 2. To determine if treatment benefits of pain coping skills are mediated by changes in pain catastrophizing:

- **Hypothesis 4.** Changes in pain catastrophizing that occur over the course of pain coping skills training will mediate treatment-related improvements in pain and self-reported function during recovery.
-

Research Strategy

Significance: Specific Aim 1

Knee arthroplasty surgery (TKA) is a common and generally effective procedure.¹ For example, projections estimate that 3.5 million procedures will be conducted annually by 2030.² Cost data for TKA also are impressive. Mean procedural charges per patient in 2003, reported in 2005 dollars, were \$38,000 per primary surgery and \$48,000 per revision surgery.³ If these procedural charges data were extrapolated to the 2010 volume data projections, procedural charges would total approximately \$28 billion dollars annually.

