A barrier to progress in this field is that traditionally, knee arthroplasty has been presumed to be a highly effective procedure. The culture in clinical practice has historically been to forgo routine screening for patients at-risk for post-surgery persistent pain or compromised function. This culture has potential for change, however, because recent research has begun to acknowledge that unexplained poor outcomes occur. Predictors of these poor outcomes following knee arthroplasty are being identified.²³⁻²⁶ Among the most consistent and powerful psychological predictors of poor outcome following knee arthroplasty is pain catastrophizing.^{17,25,27-31}

Additional impetus to address the issue of persistent pain was proposed by NIH. An NIH consensus panel was recently convened to review existing evidence on the use of knee arthroplasty surgery and to make recommendations for future research to improve the care for these patients.³² The panel placed high priority on research examining the impact of perioperative interventions for these patients. Our proposed trial would specifically target this research need. If a high-quality trial demonstrated that pain coping skills training was successful at improving outcomes for at-risk patients with poor pain coping, and was cost effective, current clinical practice paradigms could be significantly improved.

Significance: Specific Aim 2

As Vlaeyen and Morley note, an important barrier to improving the effects of pain coping interventions is the use of a “one size fits all” approach to applying the intervention.³³ Systematic reviews have consistently demonstrated the efficacy of pain coping skills training and other forms of behavioral treatment for patients with a variety of musculoskeletal disorders.³⁴⁻³⁶ However, effects generally are modest with effect sizes of 0.5 or less; a substantial proportion of patients receiving pain coping skills training do not appear to benefit.^{37,38} Vlaeyen and Morley suggested that one way of improving outcomes is to better match the behavioral treatment to patient characteristics.³³ To address this issue, we have intentionally selected for treatment a sub-group of patients with high levels of pain catastrophizing, who we hypothesize will likely experience substantial benefits from pain coping skills training.

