The primary outcome measure and endpoint will be the WOMAC Pain scale measured 1 year following knee arthroplasty.¹⁰⁵⁻¹⁰⁹ The WOMAC has been studied extensively and its scales have been shown to be reliable and valid for quantifying the extent of both pain and disability in patients undergoing knee arthroplasty.^{16,110,111} Secondary outcome measures will be the WOMAC Disability scale, Pain Catastrophizing Scale (PCS),¹¹²⁻¹¹⁴ a verbal pain rating scale,^{115,116} and a patient global rating of change scale measured on a numerical rating scale from -5 (vastly worse) to +5 (completely recovered) and measured 2 months, 6 months and 1 year post-surgery.¹¹⁷⁻¹¹⁹ The timeframes were chosen because the trajectory of recovery following knee arthroplasty is non-linear and we want to track changes associated with the intervention during the course of the study.^{10,13,94} Two performance-based measures, the 6-minute walk test^{93,98} and the Short Physical Performance Battery will be assessed at baseline and 1 year post-surgery.¹²⁰ Routine follow-up visits are typically scheduled with the surgeon at 12 months following surgery. Planning follow-up measures to coincide with routine patient visits to their surgeon or other provider will be a cost-effective and clinically feasible way of collecting follow-up data with minimal burden. All sites will have the space necessary to conduct the performance-based tests. This is the first study of a pain coping skills training intervention that has used performance-based measures to assess efficacy. This battery of primary and secondary outcomes addresses the key domains of outcomes recommended by IMMPACT, a consensus based group of experts in the area of pain treatment outcomes.^{121,122}

Sample Size Estimations

The primary endpoint will be the WOMAC Pain score at 1 year. Changes of 2 or more points in the 20 point WOMAC Pain scale indicate clinically important differences between individual patients.¹²³⁻¹²⁶ We powered our study to detect a difference of at least 2 points between the pain coping skills group and the arthritis education group. Our pilot study showed a larger difference of 4.2 points (with an effect size of .74) between the coping skills group and the usual care group two months following surgery. We will use a more conservative treatment

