effect of 2 WOMAC Pain points for coping skills training for three reasons. First, our pilot study used a quasi-experimental design which may overestimate treatment effects because of non-randomization. Second, estimates were based on comparisons to usual care, and we suspect that some therapeutic benefit will be experienced by the arthritis education group. Third, these data represent only short-term changes following surgery and most patients continue to improve up to a year following surgery.^{9,14}

Using a two-sided two group 0.05-level t-test of differences in means and assuming the intervention difference minus the arthritis education control difference is at least 2.0 WOMAC Pain points, a sample size of 107 in each group will have 91% power to detect this difference, assuming that the common standard deviation is 4.34 (based on pilot work described earlier). This corresponds to an effect size of 0.46 which is consistent with the effect of other behavioral interventions for knee arthritis.¹²⁷⁻¹²⁹ This sample size also adequately powers the study to detect a 20% difference between groups in the number of patients with a 50% or greater improvements in WOMAC pain relative to baseline scores.^{9,10,12-15,130} This effect will be equivalent to an odds ratio of 2.25 and is equivalent to a Numbers Needed to Treat (NNT) of 5 which is indicative of an effective intervention.¹³¹ The revised CONSORT statement endorses use of indexes such as number needed to treat.¹³²

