Periodic and ad-hoc reporting will be utilized to show subject recruitment and retention data stratified by site. Automated email agents will electronically notify site staff and investigators of upcoming and overdue subject follow-ups. Upon request, the data manger will provide de-identified data in a form agreeable to the biostatistician. In addition, the DMG will provide timely troubleshooting assistance via phone and email and answer inquiries from research staff and investigators. The investigators will develop a User’s Guide to aid the study staff with data management tasks should the study be funded.

Approach: Specific Aim 2

We will collect Pain Catastrophizing Scale, WOMAC Pain and Disability Scale and a verbal pain rating scale scores on all patients at six time points (4 to 6 weeks prior to surgery, 1 week prior to surgery, 1 week following surgery, 2 and 6 months following surgery and 1 year following surgery). Our rationale is that we want to capture the short- and intermediate-term temporal progression of changes in catastrophizing prior to and following treatment to describe changes in mediation over time. The primary outcome measure will be the WOMAC Pain scale, collected at all assessment points. The independent variable will be treatment condition (Pain Coping Skills Training vs Arthritis Education vs usual care). (Figure 1)

Our hypothesis is that the effects on WOMAC Pain by the pain coping skills arm will be either partially or fully mediated by pain catastrophizing, whereas effects by arthritis education or usual care will either not be mediated by pain catastrophizing or mediated to a significantly lesser extent as compared to the pain coping skills arm. Mediation will be investigated using the three-step approach described by Baron and Kenny¹⁷ and modified for randomized trials by Smeets and colleagues.¹⁴⁴ A series of 3 multilevel regression analyses will be used to determine if pain catastrophizing mediates the effect of the interventions on pain as measured with the WOMAC Pain scale at the various time points. WOMAC Disability and verbal pain rating scores will serve as secondary outcome measures for the mediation analysis.

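### Aim 2 names the three-step Baron-Kenny approach but no estimate or interval for the indirect effect, and does not say whether a significant total effect on WOMAC Pain is required first

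*Combined protocol and SAP*

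**What the plan says.** The method is in the combined protocol and SAP under Approach: Specific Aim 2: "Mediation will be investigated using the three-step approach described by Baron and Kenny", as "modified for randomized trials by" a cited group. The implementation is one sentence: "A series of 3 multilevel regression analyses will be used to determine if pain catastrophizing mediates the effect of the interventions on pain", with WOMAC Pain analysed at the several assessment times. The section does not set out the three steps, their significance criteria or the content of the modification. It names no estimate, interval or bootstrap for the indirect effect.

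The plan's questions are about size and timing:
- Significance: Specific Aim 2 wants to know how far catastrophizing mediates the treatment effect.
- Innovation: Specific Aim 2 promises to quantify the effects and their timing.
- Approach: Specific Aim 2 follows catastrophizing "prior to and following treatment to describe changes in mediation over time", and expects clearly less mediation in the other two arms.

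Hypothesis 4 says that changes in catastrophizing "will mediate treatment-related improvements in pain and self-reported function during recovery". The only power statement concerns the total effect at 1 year (Sample Size Estimations): "We powered our study to detect a difference of at least 2 points between the pain coping skills group and the arthritis education group".

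**The concern.** In the classic form of the named method, one of the three regressions is outcome on treatment, and mediation is concluded only if that total effect is significant. An indirect effect does not need this. Treatment can lower catastrophizing, and lower catastrophizing can go with less pain, while the total effect is small, imprecise or offset by another pathway. If the step is kept, the mediation answer at each visit depends partly on the power of the total-effect test at that visit.

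A set of significance checks also yields no quantity to compare between visits or between comparisons, which is what the plan says it wants. An analyst working only from this text could apply the total-effect step by default, and would have no pre-specified indirect-effect estimate to report.

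**Working it through.** **Inputs from the plan** (Sample Size Estimations): n = 107 per arm, SD = 4.34, planned difference 2.0 points. The test is set out there: "Using a two-sided two group 0.05-level t-test of differences in means". No significance level is given for the mediation steps, so 0.05 two-sided is assumed for each.

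**The plan's own figure.** Effect size 2/4.34 = 0.46, as stated. SE of the difference = 4.34 × √(2/107) = 0.593. Noncentrality = 2/0.593 = 3.37. Noncentral t with 212 df gives 91.9% power; the plan states 91%. Reproduced.

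**Chance of passing a total-effect step**, by the same formula:

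| True total effect (points) | 0.5 | 0.75 | 1.0 | 1.25 | 1.5 | 1.75 | 2.0 |
|---|---|---|---|---|---|---|---|
| Pass | 13% | 24% | 39% | 56% | 71% | 84% | 92% |

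The 50% point is about the critical t times the SE: 1.971 × 0.593 = 1.17 points, or 1.17/4.34 = 0.27 SD. It is 1.29 points with SD 4.8 (the pilot historical cohort), 1.04 with all 134 enrolled per arm, and 1.16 with both.

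**All three steps against the two paths alone.** Simulation with 107 per arm, within-arm SD of pain 4.34 and 3,000 runs per setting. The PCS-pain correlation r within arms and the mediated share are assumptions, not taken from the plan. The implied PCS effect in SD units is share × total/(r × 4.34). For example, r = 0.5, full mediation and 1.0 point gives 1/(0.5 × 4.34) = 0.46 SD. Each cell shows the percentage with all three steps significant / the percentage with both paths significant.

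| r | Share mediated | PCS effect at 1.0 point (SD) | 1.0 point | 1.5 points | 2.0 points |
|---|---|---|---|---|---|
| 0.3 | 50% | 0.38 | 32.8 / 79.3 | 71.5 / 98.3 | 91.0 / 99.6 |
| 0.3 | 100% | 0.77 | 39.1 / 99.4 | 71.0 / 99.2 | 92.0 / 99.4 |
| 0.5 | 50% | 0.23 | 24.1 / 39.8 | 58.0 / 70.8 | 86.4 / 92.2 |
| 0.5 | 100% | 0.46 | 37.4 / 91.9 | 70.7 / 99.9 | 92.5 / 100 |
| 0.6 | 50% | 0.19 | 18.9 / 27.8 | 47.7 / 55.4 | 75.5 / 78.8 |
| 0.6 | 100% | 0.38 | 37.5 / 81.5 | 71.7 / 98.5 | 92.4 / 100 |

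Simulation error is at most √(0.25/3000) = 0.9 percentage points (one standard error). The r = 0.5, full-mediation row can be checked by hand. A 0.46 SD effect on PCS has the same noncentrality (3.37) as the plan's 2-point pain effect, hence about 92% power, and the PCS-to-pain path was significant in every run.

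A second simulation fixed the PCS effect at 0.4, 0.5 or 0.71 SD (0.71 is the lower end of the pilot effect sizes). At 1.0 point it gave 26–38% with all three steps against 66–99.8% for the two paths; a repeat gave 26–39% against 65–99.9%. At 2.0 points it gave 79–92% against 83% to nearly 100%. A repeat of the 0.23 SD, half-mediated setting at 1.0 point gave 25% against 40%. Over PCS effects of 0.23 to 0.71 SD, the range at 1.0 point is therefore about 25–39% against 40–99.9%.

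**The case against.** The strongest reply is that the total-effect requirement is not written in the plan. It is inferred from the method's name, and the cited modification may have removed it. That stands: the documents show only that the matter is unspecified, so the power loss is conditional on the step being kept.

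Hypothesis 4 speaks of treatment-related improvement and so presumes an effect to explain; mechanism without a demonstrated total effect is a wider question. That is fair, but it does not supply the missing estimate of how much is mediated and when.

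The plan also gives no reason to expect a total effect below 1.2 points. Significance: Specific Aim 2 says of behavioral treatment that "effects generally are modest with effect sizes of 0.5 or less". The planned 0.46 fits that remark as well as 0.27 does, and the same section expects substantial benefit in the selected patients. However, the 2-point figure is for 1 year only, while mediation is to be examined at several visits.

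The largest contrasts come from assumed settings in which treatment moves PCS much more than pain. Where the PCS path is weak, dropping the step gains little (r = 0.6, half mediated, 1.25 points: 33% against 42%).

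A reader might also infer that a null result on pain would leave the trial unable to tell whether training reduced catastrophizing. The documents do not support this. PCS is a secondary outcome (Hypothesis 2; Primary and Secondary Outcome Measures and Endpoints), and Data Analysis treats secondary outcomes much like WOMAC Pain, with no condition on the primary result.

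**Conclusion.** The point holds as a gap in specification with a conditional cost. The Aim 2 text names no indirect-effect estimate or interval, so it does not deliver the extent of mediation or its change over time. If the classic total-effect step is kept, that step alone blocks a mediation conclusion more often than not below about 1.2 points (1.04 to 1.29 across the SD and sample sizes tried).

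A reader might infer that mediation would usually be missed for any total effect under the planned 2 points. The figures do not support that: at 1.5 points the step is passed 71% of the time, and at 2.0 the loss is small. Nor do the documents say that change over time will be read from the visits at which p < 0.05.

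The results assume 0.05 per step, one comparison at one visit, no precision gain from the multilevel model or covariates, and the stated PCS correlations, effects and mediated shares. The primary analysis is unaffected. The change is worth making because it is cheap.

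**What to change.** In Approach: Specific Aim 2:

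1. State that a significant total effect of treatment on WOMAC Pain is not required for the mediation analysis, and describe the cited modification.
2. From the same three regressions, estimate the indirect effect (treatment-to-PCS path times PCS-to-pain path) with a confidence interval, for example by bootstrap. Do this for coping skills against education and against usual care.
3. Report the two paths separately beside the total effect.
4. Judge change in mediation over time by comparing indirect-effect estimates between visits, not by noting where all three steps are significant.

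The cost is SAP wording and a little analysis code; no new data or patients are needed. The downside is interpretive: an indirect effect beside a non-significant total effect must be reported as mechanism, not as efficacy, and the SAP should say so.

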Testing for the presence of mediation (illustrated in Figure 1) will allow us to determine the extent to which pain catastrophizing^{28,29,39} mediates the relationship between pain coping skills training and outcome. The dashed

line between pain coping skills training and WOMAC Pain represents the hypothesized mediation (either partial or complete) of pain coping effects by pain catastrophizing. Understanding whether catastrophizing is a mediator for pain coping skills treatment response will provide a causative explanation for how pain coping skills training effectively improves outcomes following knee arthroplasty. If our study finds that pain coping skills training (CST) is effective and that pain catastrophizing explains these effects, the field of orthopaedic surgery could experience substantive changes in the way in which patients with knee arthroplasty are treated; to the benefit of many patients. Surgeons may begin to routinely screen for high pain catastrophizing and initiate pain

coping skills training for selected patients.

Innovation: Specific Aim 1

Current clinical paradigms do not discuss formal identification of patients at-risk for poor outcome due to poor pain coping.⁴⁰ Nor do these paradigms address the use of perioperative interventions to reduce poor outcome risk. The current application challenges this practice paradigm. If our trial is successful, as we anticipate it will be based on our pilot work, the research will provide strong evidence to reconsider this traditional approach and may improve outcomes for thousands of patients who currently are at-risk for poor outcome.

Previous work by our group²⁹ and others^{27,28,31,39} has identified a TKA patient subgroup at high risk for poor outcome. Patients with high levels of pain catastrophizing have been consistently shown to have a higher rate of persistent pain and compromised function compared to non-catastrophizers. Our study is innovative because it is the first trial, to our knowledge, to target a specific surgical subgroup of patients at risk for poor outcome. In addition, we completed a search of ClinicalTrials.gov and the World Health Organization registry portal on June 1, 2011 and found no trials examining the impact of pain coping skills behavioral interventions for patients with knee arthroplasty.

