We have modified conventional coping skills training in ways that not only make it particularly well suited to address pain catastrophizing but that are also quite innovative. Innovative features of the protocol include (1) a systematic approach to teaching patients how both the behavioral and cognitive pain coping skills they learn can be used to modify overly negative pain-related cognitions, and (2) a specific focus on helping patients who are prone to catastrophizing learn how to apply coping skills to the specific pain-related challenges associated with knee replacement surgery. Finally, studies of pain coping skills training routinely use self report outcome measures to assess effectiveness. Ours will be the first to include physical performance among our secondary measures to assess outcome, an innovative addition to outcome assessment.

Innovation: Specific Aim 2

Pain catastrophizing has been shown to mediate outcome of multidisciplinary medical treatment for chronic pain.⁵²⁻⁵⁵ The KASTpain trial will be the first to determine if pain catastrophizing plays a mediating role in the context of a perioperative pain coping skills training intervention. By quantifying effects as illustrated in Figure 1, we will provide new insights into the temporal relationship of mediation effects of pain catastrophizing in patients receiving pain coping skills training immediately prior to, immediately after and several months following surgery.

[figure not shown]
Approach: Specific Aim 1

Trial Design

The investigative team reached consensus on the final trial design during the R34 planning process. The KASTpain study will be a multi-center phase III randomized three-arm controlled trial designed to determine if pain coping skills training improves outcomes following primary knee arthroplasty to a greater extent than either an attention control arthritis education intervention or usual care.

Outcome assessors will be blinded to group assignment and patients randomly assigned to either the coping strategies training or arthritis education will be blinded to experimental group assignment to the extent that they will not be informed which group is believed to contain the key therapeutic elements (pain coping skills). Patients randomly assigned to usual care will not be blinded but assessors will be blinded to group

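### The Aim 2 mediation plan names no main time-ordered pairing, no earlier-pain covariate, and no estimator or interval for the indirect effect, although Hypothesis 4 is ordered in time

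*Combined protocol and SAP*

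**What the plan says.** The analysis is set out in the combined protocol and SAP under Approach: Specific Aim 2. Catastrophizing, WOMAC Pain and Disability, and a verbal pain rating are collected at six shared visits: 4 to 6 weeks and 1 week before surgery, then 1 week, 2 months, 6 months and 1 year after it. The purpose of so many visits is "to describe changes in mediation over time". On method, "Mediation will be investigated using the three-step approach", in a cited form "modified for randomized trials". The models are then named: "A series of 3 multilevel regression analyses will be used to determine if pain catastrophizing mediates the effect of the interventions on pain". The visits are left general, because the outcome enters these models "as measured with the WOMAC Pain scale at the various time points".

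The hypothesis itself, under Specific Aim 2, has an order in time: "Changes in pain catastrophizing that occur over the course of pain coping skills training will mediate treatment-related improvements". The improvements meant are those seen in pain and function as patients recover. Innovation: Specific Aim 2 adds that "we will provide new insights into the temporal relationship of mediation effects of pain catastrophizing". Significance: Specific Aim 2 says the analysis will show how far catastrophizing mediates the treatment effect and will give a causal account of it. It names a possible consequence: "Surgeons may begin to routinely screen for high pain catastrophizing".

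**The concern.** Catastrophizing may fall because pain falls, as well as the other way round. The pilot (Pilot Intervention Study) measured both before surgery and at 2 months and reports effects on both, so it cannot show which moved first. An analysis meant to support a causal, time-ordered claim therefore has to say which catastrophizing value comes before which pain value, and what is adjusted for.

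Hypothesis 4 does not settle the pairing. Training runs until about 1 month after surgery (Pain Coping Skills Training), so it overlaps early recovery. Catastrophizing at 1 week before, 1 week after or 2 months after surgery could each serve as the mediator.

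A series of significance tests also does not give the size of mediation that the protocol promises. If one of those tests is the total effect, the mediation finding depends on the power of the efficacy comparison. At stake are a false or missed claim about mechanism and the screening advice that might follow from it.

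**Working it through.** **1. The texts side by side.**
- Aim 1 (Data Analysis): baseline covariates are named, contrasts are of change from baseline, and the key visits are 2 months, 6 months and 1 year.
- Aim 2 (Approach: Specific Aim 2): mediator, outcomes, treatment variable and six visits are named. No main pairing, earlier-pain covariate, indirect-effect estimator or interval is given.
- The baseline covariates of Aim 1 belong to the efficacy model and are not carried over in the text.

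**2. The plan's own figure.** Sample Size Estimations gives 107 per arm, a difference of 2.0, SD 4.34 and 91% power. The effect is 2.0/4.34 = 0.461 SD. With z = effect × √(n/2) and √(107/2) = 7.314, z = 3.37. Power = Φ(3.37 − 1.96) = 92.1% (91.9% by noncentral t), close to the stated 91%. The plan gives no figure for mediation.

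**3. Cost of a total-effect condition.** The document does not list the three steps. I assume they are: treatment affects pain (total effect); treatment affects catastrophizing (path a); catastrophizing predicts pain given treatment (path b). Further assumptions are single-level models, within-arm SD 1 for both variables, and full mediation, so a × b = total effect. For path b, z = b/√(1 − b²) × √(214 − 3).

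Total effect 0.30 SD:
- total effect: 0.30 × 7.314 = 2.19, power Φ(0.23) = 59%;
- b = 0.4, so a = 0.75: path a z = 5.49 (power over 99.9%), path b z = 6.34 (over 99.9%);
- b = 0.6, so a = 0.50: path a z = 3.66 (power 95.5%), path b z = 10.9 (over 99.9%).

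The three-step rule needs all three tests, so it cannot exceed about 59%. An interval for a × b is limited only by paths a and b. Simulation gives 58-60% against 96-100%.

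At a total effect of 0.46 SD the gap is small: 91-93% against 100%. With only half the effect mediated and a total of 0.30 SD, the figures are 36-50% against 46-80%.

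**4. Same-visit pairing when pain drives catastrophizing.** Assume a total effect on pain of 0.46 SD, no true mediation, and catastrophizing = k × pain + error. The apparent path a is k × 0.46.

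| k | apparent a | z | power of a | three-step, simulated |
|---|---|---|---|---|
| 0.3 | 0.138 | 1.01 | 17% | 16% |
| 0.5 | 0.230 | 1.68 | 39% | 40% |
| 0.7 | 0.322 | 2.36 | 65% | 64% |

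The total-effect test passes in 92% of trials and path b in over 99%, so the spurious path a sets the rate. My own simulation with an interval in place of the three steps gives 18/40/66%. An interval alone therefore does not cure reverse causation.

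**5. What ordering and adjustment do.** The pairing is 2-month catastrophizing with 1-year pain, baseline-adjusted, with an interval and the same reverse mechanism. Assumed pain correlations between visits are 0.3 to 0.7.
- Without 2-month pain, false mediation is about 4-14/20-39/56-68% for k = 0.3/0.5/0.7.
- With 2-month WOMAC Pain and verbal rating added, it is 0.3-1/1-4/3-13%.
- There is a price. If true mediation is already complete by 2 months, the model without 2-month pain finds it in 54-99% of trials, but both models agree in only 2-9%.

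**The case against.** The strongest reply is that the plan may be fuller than the visible text. The mediation diagram (Figure 1) is not shown. The modification for randomized trials is cited but not described. Either could set lags, covariates or drop a total-effect condition. That stands, and it limits the point to what this document states.

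Other parts of the reply also stand. An estimate of some kind is intended, because the Significance and Innovation sections speak of the degree of mediation and of quantifying effects; what is missing is the estimator and its interval. Hypothesis 4 defines the mediator as a change, so baseline catastrophizing enters by definition. Describing mediation over time is a stated aim, so analysing several visits is not itself a fault. It does not, however, choose a main test.

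A reader might infer that the plan pairs same-visit values, and so faces the false-positive rates in step 4. The documents do not say so, and the order in Hypothesis 4 points away from it. A reader might also infer that a significant total effect is definitely required. That too cannot be established without the cited source.

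Finally, 2-month pain is measured after treatment and may lie on the causal path. Adjusting for it is a judgement, and a rule that both models must agree would nearly rule out confirming early mediation.

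**Conclusion.** The concern holds in this limited form. The document gives a concrete method for Aim 2 but no main time-ordered pairing, no earlier-pain covariate, and no estimator or interval for the indirect effect, while promising the extent and timing of mediation.

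The clearest cost is conditional. If a significant total effect is required, detection of full mediation at 0.30 SD falls from 96-100% to about 58-60%. If same-visit values are paired, reverse causation can be declared as mediation. Both results rest on assumed paths and single-level models, whereas the plan specifies multilevel ones; the documents give no catastrophizing-pain correlation. The figures show direction and possible size and do not estimate bias in this trial.

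Ordering the visits and using an interval improves the analysis but does not exclude reverse causation. The primary efficacy analysis is untouched.

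**What to change.** Amend Approach: Specific Aim 2 as follows.
- For each contrast (training vs education, training vs usual care), estimate the indirect effect with a bootstrap 95% CI in place of the three-step significance rule. Do not require a significant total effect.
- Name one main time-ordered pairing. One example is catastrophizing at 2 months, the first visit after the last session, with WOMAC Pain at 1 year, the primary endpoint. Adjust for baseline catastrophizing and baseline WOMAC Pain.
- Add a sensitivity analysis that also adjusts for 2-month pain. State that without it reverse causation is not excluded, and that with it only mediation of later pain change is tested. Set no rule that the two models must agree.
- Label all other pairings descriptive, which keeps the aim of following mediation over time.
- State which lags, covariates and conditions the cited modification imposes.

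The cost is SAP wording and modest programming, since every measure is already scheduled. The downside is slightly more analysis and a more cautious conclusion.
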